1.0 PROTOCOL SCHEMA

Women with suspected epithelial ovarian cancer scheduled to undergo surgical exploration

Baseline evaluation

Physical examination

Serum specimens^a

RANDOMIZE

FWGE orally daily for up to 4 weeks^b

Placebo orally daily for up to 4 weeks^b

Toxicity and Quality of Life monitoring weekly and day of surgery according to NCI-CTC^c and QoL^d

At surgery: serum^{a,e} and tissue specimens^f

^aSerum CA125 at enrollment and the day of surgery

^bSurgery should be completed up to 4 weeks after beginning drug/placebo.

^cNational Cancer Institute's Common Toxicity Criteria

^dQuality of Life Survey (QoL) – FACT-O

^eDetermine the presence of 2,6-dimethoxy-p-benzoquinone in the serum

^fHistologic analysis of tissue analyzing for changes in proliferation. Gene microarray assessing for changes in gene expression

2. HYPOTHESIS and OBJECTIVES

2.1 Hypothesis

Fermented Wheat Germ Extract (FWGE) has activity against epithelial ovarian cancer (OVCA). FWGE may increase sensitivity to chemotherapy and may decrease side effects related to chemotherapy. FWGE active components (2,6-dimethoxy-p-benzoquinone) may be detected in serum of women receiving FWGE.

In an effort to generate preliminary data to support a future peer-reviewed grant-funded large phase II clinical trial of adjuvant FWGE in women undergoing therapy for ovarian cancer and to test the safety and tolerability of FWGE, we propose a pilot randomized, placebo-controlled study of FWGE in women with a suspected diagnosis of OVCA. We propose to test the safety and tolerability of FWGE, and to determine if we can detect an active product of FWGE (2,6-dimethoxy-p-benzoquinone) in the serum, and whether short-term therapy with FWGE has an effect on the tumor marker, CA125. We will analyze changes in tissue proliferative assays and gene expression in women who receive FWGE (n=10) and those who receive placebo (n=10).

We recognize that the sample size in the current study will prohibit definitive statistical conclusions to be drawn on our primary objective (to test the safety and tolerability of FWGE), or our secondary objectives (to compare levels of FWGE active product, CA125 levels, proliferation, and gene expression in OVCAs from subjects receiving FWGE versus placebo). The study is neither designed nor powered to develop statistically significant results, rather, we seek to develop preliminary/pilot data that will enable us to pursue a future large phase II, peer-reviewed grant-funded trial of adjuvant FWGE in women undergoing therapy for ovarian cancer. Preliminary data developed in the current proposal will support such grant applications.

2.2 Objectives

2.21 Primary Pilot Objective: To assess the safety, toxicity and quality of life (QoL) of women with suspected ovarian cancer scheduled to undergo surgery, administered FWGE versus placebo daily for up to 4 weeks.

2.22 Seconday Pilot Objectives:

2.221 To develop pilot data on the impact of FWGE on: the tumor marker CA125, tumor proliferation.

2.222 To develop pilot data on changes in gene expression in ovarian cancer exposed to FWGE versus placebo.

3.0 BACKGROUND AND RATIONALE

3.1 Ovarian Cancer

Ovarian cancer (OVCA) is the 5th leading cause of cancer death among women in the United States and Europe and has the highest mortality of all gynecologic cancers. It is estimated that 21,980 women in the U.S. will be diagnosed with epithelial OVCA in 2014 and 14,270 women will die of the disease [1]. Approximately 75% of cases are diagnosed at an advanced-stage (III/IV) with disseminated intraperitoneal metastasis [2]. Women with OVCA undergo major surgery followed by chemotherapy in an attempt to prolong survival. Although approximately 70% of women will demonstrate a clinical response to this primary therapy, the majority will develop progressive or recurrent disease that is platinum-resistant. Women with platinum-resistant OVCA often demonstrate cross-resistance to most other chemotherapeutic agents. Once platinum-resistance has developed, few active therapeutic options exist and patient survival is generally short-lived. Throughout treatment for OVCA, prolongation of survival and the successful maintenance of quality of life remain important goals. Improving our ability to manage the disease by optimizing the use of existing drugs and/or developing new agents is therefore essential in this endeavor.

3.2 Use of natural products

Up to 90% of patients with cancer use alternative therapies, often herbal or natural products [3,4]. The majority of these products have not been subjected to comprehensive study for efficacy or potential negative interactions with chemotherapy. Natural, non-toxic regimens that enhance standard-of-care therapy and/or prolong survival are highly desirable in management of patients with cancer.

3.3 Fermented Wheat Germ Extract

Fermented wheat germ extract (FWGE, Avemar®) was developed in Hungary in the early 1990's [5]. It is produced by extraction of wheat germ, fermentation of the extract, separation of the fermentation liquid, concentration, and drying. The chemical composition of FWGE is a mixture of molecules including 2-methoxy-p-benzoquinone and 2,6-dimethoxy-p-benzoquinone, which are felt to contribute to its biological properties [6]. FWGE has been available as a dietary supplement in Hungary since 1998 and was approved in 2002 as a "medical nutriment for cancer patients." It is classified by the European Union as a "dietary food for special medical purposes". FWGE has been shown to be safe when taken orally with no toxicity, mutagenicity, or genotoxicity [6].

3.31 In Vitro Studies

FWGE has been evaluated in-vitro and shown to induce apoptosis in some cancer cell types, including: leukemia, breast, colon, testicular, head and neck, cervical, ovarian, gastric, thyroid, melanoma, brain and hepatocellular carcinomas [7-10]. The addition of FWGE to 5-fluorouracil, oxaliplatin or irinotecan chemotherapy has been shown to have no negative impact on effectiveness or toxicity profiles, and in colon cancer cell lines has additive to synergistic effects [7].

With this data suggesting that FWGE has activity against many cancer cell types, we studied the broader spectrum of activity against OVCA.

3.32 Our Ovarian Cancer In Vitro Studies [11]

Our in-vitro data demonstrates that FWGE induces OVCA cell line growth arrest and apoptosis and that it sensitizes OVCA cells to cisplatin-induced cell death. We also have data to suggest that the sensitivity of OVCA cells to FWGE may be determined by a discrete number of molecular signaling pathways.

FWGE induces growth arrest and cell death in ovarian cancer cell lines

We evaluated the effects of FWGE on cell growth arrest in a panel of 12 OVCA cell lines using MTS cell viability assays (Fig 1). Several of these cell lines were paired, mother/daughter, sensitive/resistant lines. Notably, cisplatin-resistance, a surrogate marker of greater chemotherapy-resistance, did not predict FWGE sensitivity. This

suggests the biologic determinants of resistance to chemotherapy agents may differ from those that influence response to FWGE.

for each cell line is shown numerically in ug/ml.

FWGE

potentiates chemotherapy (cisplatin)-induced cell death

To determine if FWGE and the chemotherapy agent cisplatin work synergistically to induce OVCA cell growth arrest, we evaluated 100 and 200 ug/ml FWGE in combination with cisplatin (190, 390, 780, and 1,560nM). Drug activity was evaluated using the combinational index (CI) value determined by the Chou-Talalay isobologram equation where CI<1, CI=1, and CI>1 indicate synergistic, additive, and antagonistic effects. As shown in Figure 2 the majority of FWGE/cisplatin combinations showed greater than additive effects while several combinations were strongly synergistic.

[figure not shown]

Figure 2. Combinational index (CI) values of FWGE and cisplatin drug activity in OVCA cells. CI values of CI<1, CI=1, and CI>1 indicate synergistic, additive, and antagonistic effects.

Expression of genes and signaling pathways that correlate with FWGE sensitivity in OVCA cells

To better understand the mechanisms that underlie FWGE activity in OVCA cells, Affymetrix gene expression data from the 12 cell lines was correlated with FWGE IC50. Using SAM'S Correlation Test (FDR<20%) identified 40 genes associated with FWGE sensitivity in Table 1. In order to place these genes into a relevant biologic

context, an analysis of biologic pathway relationships was performed using commercially available software (GeneGo Meta-Core™, (genego.com). GeneGo identified 16 pathways represented by genes associated with FWGE sensitivity p≤0.05. As described above, one of the active components of FWGE is thought to be 2,6-dimethoxy-p-benzoquinone. Analysis of publically available Affymetrix expression data (http://discover.nci.nih.gov/cellminer/loadDownload.do) and NCI60 cell line GI50

ZNF254	ZNF708	COPG2	SHF	tcag7.1228	SLC25A13	ZCCHC17	DYNC2LI1	GPATCH2	FAM133B
ARL5B	FAM117B	NRF1	PHF21A	POLR2J	SOX12	DBF4	FMC1	KLHL7	DUXAP10
LSM8	PHF21A	SLC7A7	SMAD2	SMARCD1	SUZ12P	ZBTB44	ZFP106	TRIM24	RPE
ZNF322A	ZSCAN21	ACVR2B	APOC1	C10orf111	C20orf74	MIDN	PLXND1	AGFG1	CCDC5

Table 1. Genes correlated with FWGE sensitivity

values for 2,6-dimethoxy-p-benzoquinone

(http://dtp.nci.nih.gov/dtpstandard/cancerscreening data/index.jsp), identified 3839 genes representing 267 pathways associated with sensitivity to 2,6-dimethoxy-p-benzoquinone (data not shown). Comparison of signaling pathways correlated with sensitivity to FWGE in OVCA cells and 2,6-dimethoxy-p-benzoquinone in NCI60 cell lines identified 9 common biological pathways

3.33 In Vivo Studies

FWGE has been shown *in vivo* to decrease metastatic spread of cancer, decrease carcinogenesis and to be non-toxic and non-inhibitory when administered with chemotherapy.

Synchronous oral FWGE and 5-fluorouracil intraperitoneal delivery significantly reduced the metastatic spread of c38 colorectal cancer in mice. [12]

In a study on F-344 rats, the administration of azoxymethane induced colon carcinogenesis. When FWGE was fed to the rats prior to the azoxymethane administration, significantly fewer rats developed colon tumors (83% vs 45% p< 0.001) [13]

In vivo, FWGE was administered in mice simultaneously with cyclophosphamide,

vinorelbine, or doxorubicin. There was no increased toxicity or decreased antiproliferative activity [14].

3.34 Human Clinical Studies

When taken orally in addition to chemotherapy, FWGE has been shown to decrease adverse events, inhibit cancer cell proliferation and metastatic spread, and increase overall survival in patients with colorectal cancer and melanoma.

One hundred and seventy-six colorectal cancer patients with histologically confirmed (Dukes A–D) colorectal cancer were enrolled. No restrictions were made for prior radiotherapy and/or chemotherapy, but all the patients had to undergo curative surgery at the time of diagnosis. There was no randomization; cohorts were formed based on patient preference. FWGE was taken orally once daily. Patients received adjuvant therapy by physician preference. No grade 3 or 4 adverse events were observed. Patients receiving FWGE had a significant prolongation of progression free survival (p = 0.0184) and overall survival (p = 0.0278) [15] A trial performed in pediatric patients with solid malignancies undergoing chemotherapy was conducted to assess whether the combined administration of FWGE with chemotherapy would reduce the incidence of treatment-related febrile neutropenia. Twenty-two patients were enrolled; they were not randomized, but allowed to choose their treatment arm. The patients were matched by diagnosis, stage of disease, age, and gender. During the treatment period, there was no progression of the malignant disease. The frequency of febrile neutropenia was significantly decreased in patients receiving FWGE: 30 febrile neutropenic episodes (24.8%) in the FWGE group versus 46 (43.4%) in the control group (p < 0.05) [16]

An open-label, randomized, phase II trial to assess the supportive value of FWGE in patients with stage III melanoma scheduled to receive adjuvant therapy was performed. Post-operatively, patients were randomized to FWGE simultaneous with adjuvant dicarbazine (DTIC) and FWGE continued for 12 months or DTIC alone. Fifty-eight patients were enrolled. Three from each treatment arm withdrew from study, for 52 patients analyzed. Adverse events included: grade1 and 2 nausea/vomiting, and grade 1 diarrhea. There were no grade 3 or 4 adverse events. They noted fewer toxic side effects in patients receiving the FWGE than in those of

the control group. There was a statistically significant improvement in progression-free survival 55.8 months (FWGE) versus 29.9 months (control) p = 0.0137. There was a statistically significant improvement in overall survival of 66.2 months (FWGE) versus 44.7 months (control) p = 0.0298 [17].

3.35 Summary and Rationale:

Fermented wheat germ extract has been demonstrated in vitro to induce ovarian cancer cell growth arrest and apoptosis. When FWGE is combined with cisplatin chemotherapy it enhances cell killing. In animal studies, FWGE has shown no toxicity and anticancer effects. Observations from human clinical trials demonstrate FWGE to be safe and without serious adverse events. The data also suggest beneficial effects of FWGE on disease progression and survival in patients with melanoma and colorectal cancer.

3.4 Proposal Overview: In this pilot clinical trial, we will evaluate the safety, toxicity and quality of life (QoL) of ten women with ovarian cancer scheduled to undergo surgery, administered FWGE versus ten women receiving placebo daily for up to 4 weeks. We hypothesize that FWGE will be safe and non-toxic and that administration may decrease some of the symptomatology associated with ovarian cancer. As secondary objectives, we will seek to determine whether we can detect differences in levels of 2,6-dimethoxyp-benzoquinone (one of FWGE's active products), in the serum of women receiving FWGE versus placebo. We will also evaluate the impact of FWGE on the tumor serum marker CA125, as well as histologic tumor proliferation and gene expression in ovarian cancer. As noted above, we recognize that the sample size in the current study will prohibit definitive statistical conclusions to be drawn on our primary objective (to test the safety and tolerability of FWGE), or our secondary objectives (to compare levels of FWGE active product, CA125 levels, proliferation, and gene expression in OVCAs from subjects receiving FWGE versus placebo). The study is neither designed nor powered to develop statistically significant results, rather, we seek to develop preliminary/pilot data that will enable us to pursue a future large phase II, peer-reviewed grant-funded trial of adjuvant FWGE in women undergoing therapy for ovarian cancer. Preliminary data developed in the current proposal will support such grant applications.

3.5 Rationale for the Dosage Used in this Study

The dose of FWGE that has been chosen for the study, is the dose used in each of the three previous clinical trials. This consists of 5.5 grams of FWGE formulated as a water-soluble granulate with added 0.03 grams of stevia sweetener and orange flavorings (taking it to approximately 5.53 grams), dissolved in 150 mL of water, orally once-daily.

This dose has been tolerated well in previous clinical trials with no grade 3 or 4 toxicity, even when combined with chemotherapy.

With regard to length of the intervention, most patients are scheduled for surgery within 4 week interval. We do not want to delay a patient's surgery for the intervention.

4. PATIENT ELIGIBILITY

4.1 Inclusion Criteria

- 4.11 Women with suspected epithelial ovarian, fallopian tube or primary peritoneal carcinoma scheduled to undergo surgical exploration with no prior treatment for the cancer. Signs of ovarian cancer include, but are not limited to: an elevated CA125, a complex pelvic mass, ascites, and carcinomatosis. These signs are not necessary for suspicion or enrollment in this protocol.
- 4.12 Age > 18 years and competent to give informed consent
- 4.13 Patient must have a ECOG Performance sttus of 0, 1, or 2 and a life-expectancy of at least 60 days.
- 4.14. Patients must have adequate:
 - 4.141 Bone marrow function: Hemoglobin greater than or equal to 9gm/dl. Absolute neutrophil count (ANC) greater than or equal to 1,500/ul, equivalent to Common Toxicity Criteria (CTCAE v4.0) grade 1. Platelets greater than or equal to 100,000/ul.
 - 4.142 Renal function: creatinine less than or equal to 1.5 x institutional upper limit normal (ULN), CTCAE v4.0 grade 1.

- 4.143 Hepatic function: Bilirubin less than or equal to 1.5 x ULN (CTCAE v4.0 grade 1). SGOT and alkaline phosphatase less than or equal to 2.5 x ULN (CTCAE v4.0 grade 1).
- 4.15 Study subjects must sign an approved informed consent and authorization permitting release of personal health information.
- 4.16 Women of childbearing potential must have a negative serum pregnancy test prior to the study entry and be practicing an effective method of birth control during the course of the study, in a manner such that risk of failure is minimized. Prior to study enrollment, women of childbearing potential must be advised of the importance of avoiding pregnancy during trial participation and the potential risk factors for an intentional pregnancy.

4.2 Exclusion Criteria

- 4.21 Current use of FWGE
- 4.22 Known allergy to wheat, rice (contained in the placebo), orange or the sweetener, Stevis
- 4.23 Patient who received neoadjuvant chemotherapy for ovarian cancer
- 4.24 An upper gastrointestinal or other condition that would impair swallowing or absorption of oral medication
- 4.25 Any serious illness or medical condition that would not permit the patient to be managed according to the protocol, including, but not to limited, any the following:
 - History of significant neurologic or psychiatric disorder (e.g., uncontrolled psychiatric disorders) that would impair the ability to obtain consent or limit compliance with study requirement

- Active uncontrolled or serious infection
- Active peptic ulcer disease
- 4.26 Uncontrolled hypertension defined as systolic greater than 180 and diastolic greater than 100

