5. STUDY MODALITIES

5.1 FWGE

- 5.11 Formulation: American BioSciences Inc, who is the exclusive manufacturer of FWGE in the Unites States, produces fermented wheat germ extract. See Letter of Support (Appendix II). It is formulated as a granulate. One package contains 5.53 grams of FWGE combined with natural orange flavor and stevia Reb-A sweetener to create an instant drink mix. See compositional analysis (Appendix III).
- 5.12 Administration: FWGE is dissolved in 150ml water and taken orally daily.
- 5.13 Adverse effects

The clinical safety experience of FWGE is derived from trials in which FWGE has been used as a single agent or in combination with chemotherapeutic agents. FWGE has not been associated with any grade 3 or 4 toxicities

- 5.14 Storage: FWGE is to be maintained at <80 degrees F
- 5.15 Quality assurance of the manufacturing of FWGE in the U.S.
 - 5.151 The purchased wheat germ and yeast, which are the raw materials of FWGE production, are certified for human consumption. The origin of the wheat germ and yeast, used in the fermentation, are all U.S. certified.

- 5.152 After each batch of FWGE has been freeze-dried, it is tested for hazardous contaminates, such as toxic elements, including heavy metals, and for toxic microorganisms, such as E.Coli, Listeria, etc. Once, the lyophilizate has been found free from toxic contaminants, and has been qualified as microbiologically safe (such as complete lack of toxic micriorganisms, etc.), it is standardized to ensure batch-to-batch chemical compositional homogeneity and biological efficacy-related reproducibility.

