7. TREATMENT MODIFICATIONS

- 7.1 It is expected that the dose of FWGE used in this study will be well tolerated; therefore there will be no dose modification. Specimens will be collected from all patients who undergo surgery even if they do not complete the full course of medication.
- 7.2 Criteria for removal from study:
 - 7.31 Patient refusal to continue treatment.
 - 7.32 Patient non-adherence to study plan.
 - 7.33 Pregnancy
 - 7.34 Patient does not have surgery within 2 months of starting FWGE or placebo.
 - 7.35 Grade 3 or 4 allergic reaction to FWGE or placebo

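### Exclusion 4.22 screens for allergy to wheat, rice, orange and the sweetener but not to yeast, which section 5.151 names as a raw material of FWGE

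*Combined protocol and SAP*

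**What the plan says.** Section 4.22 is the only eligibility criterion that deals with allergy. It excludes "Known allergy to wheat, rice (contained in the placebo), orange or the sweetener, Stevis". The remark in brackets shows that the list was meant to cover both arms, since rice is in the placebo only.

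Section 5.151, on manufacturing quality, refers to "The purchased wheat germ and yeast, which are the raw materials of FWGE production" and adds: "The origin of the wheat germ and yeast, used in the fermentation, are all U.S. certified". Section 3.3 describes the process: "It is produced by extraction of wheat germ, fermentation of the extract, separation of the fermentation liquid, concentration, and drying".

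Two other provisions come near the point. Section 4.25 excludes "Any serious illness or medical condition that would not permit the patient to be managed according to the protocol", followed by examples that are stated not to be exhaustive. Section 7.35 removes a woman from the study after a "Grade 3 or 4 allergic reaction to FWGE or placebo".

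**The concern.** The list in 4.22 goes allergen by allergen, and a screener will naturally read it as complete. One of the two named raw materials of the active product is not on it. A site applying 4.22 as written would record a woman with known yeast allergy as eligible, and she would then have an even chance of taking FWGE daily until the day before surgery.

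What is at stake is her safety. If yeast-derived material is present in the granulate, the hazard could have been identified from her allergy history before randomization. After entry, the only allergy-specific protection is 7.35, which requires a grade 3 or 4 reaction. Section 7.1 provides for no dose modification, so no allergy-specific provision covers a milder reaction.

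**Working it through.** No arithmetic decides this point, and the plan has no figure to reproduce. The check compares every material the protocol names for either product with the list in 4.22.

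| Material | Where named | Product | Covered by 4.22? |
|---|---|---|---|
| Wheat germ | 3.3, 5.151 | FWGE | Yes, as wheat |
| Yeast | 5.151 | FWGE | **No** |
| Rice | 5.21 | Placebo | Yes |
| Orange flavor | 3.5, 5.11, 5.21 | Both | Yes |
| Stevia sweetener | 3.5, 5.11, 5.21 | Both | Yes |

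Yeast is the only named material left out.

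**Does another criterion exclude her?**

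- Sections 4.11 to 4.16 and 4.21 to 4.26 do not mention yeast, and none apart from 4.22 mentions allergy.
- Section 4.25 could be used, because its examples are open-ended. It depends on the investigator's judgement and is limited to serious illness or conditions that prevent management under the protocol. With a dedicated allergy list three items above it, a screener has little reason to look there for a further allergen.
- Section 7.35 is not a screen. It operates after exposure, and only at grade 3 or 4.

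**Is yeast in the finished granulate?** The text available does not settle this.

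- The process in 3.3 includes a separation step, which may remove yeast. It does not say whether soluble yeast-derived material stays in the liquid that is then concentrated and dried.
- The batch tests in 5.152 cover hazardous contaminants and toxic microorganisms. Those in 5.153 to 5.155 cover the chemical fingerprint, the marker content and biological potency. None is described as a test for residual yeast.
- Section 5.11 refers to a compositional analysis in Appendix III, which is not in the text available for this review. That is no fault of the plan, but it is the document that would answer the question.

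**Size.** The documents give no prevalence of yeast allergy. As an assumption, take 0 or 1 such women among the 20 enrolled. With equal allocation, the expected number given FWGE is 0 × 1/2 = 0 to 1 × 1/2 = 0.5. If one woman in the FWGE arm of 10 did react, the observed count would go from 0/10 to 1/10. That needs four things together: she enrols, she is allocated FWGE, enough allergen remains, and she reacts. The documents quantify only the second.

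**The case against.** The best counter-argument is that a production input is not the same as a packet ingredient. Section 5.151 is about manufacturing quality. The packet contents are given in 5.11 (FWGE, orange flavor, stevia) and 5.21 (rice, orange flavor, stevia), and neither mentions yeast. On this view 4.22 already matches what women swallow. Part of this stands: nothing in the documents says that yeast is in the finished product, so exposure cannot be asserted. But it does not justify the list as written. Section 5.11 does not list wheat as a separate packet ingredient either; wheat is in 4.22 because the extract is made from wheat germ. The same reasoning brings in the other raw material until the protocol says why it should not.

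It can also be said that 4.25 is non-exhaustive, and that sections 3.5 and 5.13 report no grade 3 or 4 toxicity with FWGE. Both are true. The first gives discretion, not a rule. The second is weak reassurance, because the protocol does not say whether anyone with yeast allergy took part in the earlier trials.

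A reader might infer two stronger conclusions that the documents do not support.

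- *That the gap biases the primary toxicity comparison, because yeast is named for FWGE only.* In a randomized, placebo-controlled comparison, an allergic reaction caused by FWGE is a real FWGE toxicity, and counting it is correct. Placebo can also cause allergic reactions through its own ingredients. The protocol itself says in 2.1 and 12.1 that the sample size rules out definitive conclusions on safety.
- *That any such reaction would lead to removal under 7.35.* Only grade 3 or 4 reactions do.

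**Conclusion.** The gap is real and rests on the text alone: 5.151 names yeast as a raw material of FWGE, 4.22 does not list it, and no other specific criterion excludes a woman with known yeast allergy. It should be corrected because it is an avoidable potential risk that can be identified at screening. It is not a proven exposure, since residual yeast material in the granulate is neither shown nor ruled out in the available text.

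The size is small, probably 0 or 1 women, and that figure is an assumption. The point has no bearing on the sample size, the endpoints or the analysis method. The conclusion would change if the compositional analysis showed that no yeast-derived material remains. The omission would then be justified and would only need explaining.

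**What to change.** Reconcile 4.22 with the component and raw-material statements in 5.11, 5.151 and 5.21 and with the compositional analyses in Appendices III and IV. Then do one of two things:

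- add known yeast allergy to 4.22, and to the eligibility checklist so that sites apply the same list; or
- if the compositional analysis shows that no yeast-derived material remains in the granulate, say so in the protocol and leave 4.22 without it.

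The cost is one word or one sentence and a check of an appendix that the protocol already cites. The downside is a negligible effect on accrual.
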